1.1. Study rationale

This Statistical Analysis Plan (SAP) explains in detail the statistical analyses that will be carried out for PharmaMar PM104-B-003-10 study. The analyses described in this SAP are based upon and supplement those described in the study protocol (dated 30-07-2010).

1.2. Information on study drug

PM00104 is a new synthetic alkaloid that has been selected for clinical development based on its *in vitro* activity against human solid and non-solid tumor cell lines, its *in vivo* activity in xenografted human tumors, as well as an acceptable non-clinical toxicology profile.

2. Objectives

The study protocol states the following:

2.1. Primary

• To determine the antitumor activity of Zalypsis® administered as a 1-hour intravenous (i.v) infusion on Day 1, 8 and 15 every four weeks (d1, d8 and d15; q4wk) to patients with advanced and/or metastatic Ewing family of tumors (EFT).

2.2. Secondary

- To determine time-to-event efficacy parameters.
- To characterize the safety profile and tolerability of Zalypsis® in patients with unresectable advanced and/or metastatic EFT.
- To characterize the pharmacokinetics (PK) of Zalypsis® when administered as a single-agent to patients with EFT.
- To determine the pharmacodynamic profile by measuring the effect of Zalypsis® on the number of Ewing's sarcoma circulating tumor cells (CTCs) at different times of treatment and its correlation with the clinical outcome.
- To determine the pharmacogenomic (PGx) profile. Hypothesis-generating exploratory PGx analyses will be conducted to correlate the molecular parameters found in the tumor and blood samples of the patients with the clinical results achieved with Zalypsis[®].

3. Study design

Multicenter, open label, phase II clinical trial with single-agent PM00104 given as a 1-hour i.v. infusion on d1, d8 and d15, q4wk, to patients with advanced and/or metastatic EFT who failed at least to one line of standard chemotherapy.

The primary endpoint of the study is the overall response rate (ORR), defined as the percentage of patients with objective response (OR), either complete response (CR) or partial response (PR), as defined by the Response Evaluation Criteria in Solid Tumors (RECIST) v1.1.

4. Study populations

4.1. Analysis populations

Patients with EFT progressing after at least one line of standard treatment with systemic chemotherapy are eligible for this trial. To be included in the study, patients have to fulfill all inclusion criteria and none of the exclusion criteria.

4.1.1. Efficacy population

To be evaluable for efficacy, eligible patients must have received at least four infusions of the six infusions corresponding to the first two cycles and have at least one disease measurement recorded not less than six weeks after treatment onset.

In addition, any eligible patient who receives at least two of the three infusions in one treatment cycle and develops disease progression or dies due to progressive disease (PD) prior to response evaluation will be considered evaluable for the main endpoint (ORR) and will be categorized as an "early progression".

Patients withdrawn due to toxicity without any tumor assessment after the start of study treatment will be considered as "treatment failures" and will not be replaced.

Patients withdrawn due to significant clinical deterioration of unknown reason, or due to hypersensitivity reactions or unrelated AEs, and patients who refuse to continue on study for any reason without any tumor assessment after the start of study treatment will be considered not evaluable for efficacy and will be replaced.

4.1.2. Safety population

All patients who have received at least one total or partial infusion of Zalypsis® will be included in the safety analysis.

5. Endpoints

5.1. Primary endpoints

• Overall response rate (ORR): is defined as the percentage of patients with confirmed OR, either CR or PR response according to the RECIST v1.1.

5.2. Secondary endpoints

- Duration of response (DOR): is defined as the time between the date when the response criteria (PR or CR, whichever is reached first) are fulfilled and the first date when disease progression, recurrence or death is objectively documented (taking the smallest measurements documented since the treatment started as reference for PD). DOR censoring rules are the same as for progression-free survival (PFS) and are described below.
- Progression-free survival (PFS): is defined as the time from the date of the first study drug administration to the date of documented progressive disease (PD) by RECIST v1.1 or death (regardless of the cause of death). If the patient receives further antitumor therapy before PD and within the timeframe expected for first follow-up, PFS will be censored on the date of the last disease assessment prior to the administration of this antitumor therapy. If the patient is lost to follow-up for the assessment of progression, or has more than one

missing follow-up between the date of last tumor assessment and the date of progression, death or further antitumor therapy, the PFS will be censored at the date of last valid tumor assessment before the missing evaluations. PFS at three and PFS at six months (PFS3 and PFS6) are defined as the Kaplan Meier estimates of PFS at these time points.

- Overall survival (OS): is defined as the time from the first day of study treatment administration to the date of death (or the last date when the patient is known to be alive). Survival will be followed every three months until death, or until the date of study termination, whichever occurs first. OS at 12 months (OS12) is defined as the Kaplan-Meier estimates of OS at this time point.
- Safety profile: adverse events (AEs), serious adverse events (SAEs), laboratory evaluations, deaths and the reason for study discontinuations, dose delays, modifications or omissions will be analyzed. All AEs and SAEs will be classified according to the NCI-CTCAE, v4.0, and will be coded using the Medical Dictionary for Regulatory Activities (MedDRA).

5.3. Other endpoints

- Treatment exposure:
 - Date of treatment start: Date of treatment administration in Cycle 1.
 - Date of last dose: Date of last treatment administration in the last cycle.
 - *End of treatment:* Day of the last study drug administration plus 30 days, or onset of subsequent therapy or death, whichever occurs first.
 - Time on treatment: Time from treatment start to the "end of treatment" date.
 - *A cycle*: Period of time (planned as 4 weeks plus the potential administration delays) between two dose infusions. *The duration of the last cycle* (for the purpose of exposure calculations) will be 4 weeks. Therefore, the *exposure duration* will be calculated as the time between the day of the first dose and the day of last dose + 4 weeks (28 days) (expressed in weeks).
 - Body Surface Area (BSA): The calculated surface of a human body (expressed in m²). BSA will be calculated using the Dubois & Dubois formula:

$$BSA(m^2) = 0.007184 \times weight(kg)^{0.425} \times height(cm)^{0.725}$$

- *Total cumulative dose*: The sum of all the study drug doses from the first cycle until last cycle, including the dose received in last cycle (expressed in mg/m²).
- *Absolute dose intensity:* The actual cumulative dose divided by number of weeks of exposure (expressed in mg/m²/wk).
- *Intended dose intensity*: The planned dose per cycle divided by the planned weeks by cycle (expressed in mg/m²/wk).
- *Relative dose intensity:* The ratio of absolute dose intensity (x100) divided by the intended dose intensity (expressed in percentage).
- Pharmacokinetic (PK) and pharmacodinamic profile.
 - These analyses will be described in different documents not included in this SAP. For further details please refer to the study Protocol.
- Pharmacogenomic (PGx) profile.
 - The PGx analysis will be described in a different document not included in this SAP. For further details please refers to the study Protocol.

6. Sample size

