7.4.2. Cycle delays, skipped doses and dose modifications

Patients who receive only one infusion of Zalypsis[®] and have treatment discontinuation within the first cycle due to any reason different from drug related adverse event (eg: disease progression, patient's refusal), will not be considered for the calculations of the number of dose administration delays, doses skipped or dose reductions.

Dose delay is defined by a delay in the administration of the first infusion of one cycle (Day 1 infusion). Infusions not administered on Days 8 and/or 15 of the cycle are considered skipped doses and are analyzed separately.

The item "Dose delayed: No/Yes" in the case report form (CRF) will be used to calculate the delay. For doses considered as delayed by the investigator, the delay will be calculated as:

Administration delay (in days) will be equal to the date of start of the actual cycle minus the date of start of previous cycle minus 28 days (planed cycle duration, in days).

A second analysis taking into account the drug administration dates rather than the item "dose delay" completed by the investigator will be performed in order to know the calculated delay in days.

The first cycle is excluded from all calculation of cycle delay (and the denominator used for calculations will be equal to the number of cycles susceptible to be delayed).

The distribution of delays will be studied by means of counts and percentages (the denominator used for calculations will be equal to the number of patients/cycles susceptible of delay). The reasons for infusion delay will be detailed, specifying how many were due to treatment and how many were not. Within delays attributable to treatment, hematological and non-hematological reasons will be outlined, and the specific reasons will be detailed (administrative reasons will be analyzed separately and additional tables will be prepared after exclusion of those delays).

Skipped dose or dose omission is defined as every infusion not administered on Day 8 and/or 15 of the cycle. The distribution of skipped doses will be studied by means of counts and percentages (the denominator used for calculations will be equal to the number of patients/cycles susceptible to have an omission) and a detailed listing of patients with skipped

dose and reason will be showed. Also reasons for dose omission will be detailed, specifying how many were due to treatment and how many were not.

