12.1. Extent of exposure

12.1.1. Treatment administration

Table 12.1.1.1 Cycles administered.

Cycles per patient: n (%)	N	0/0
1		
2		
3		

Table 12.1.1.2 Summary of cycles administered.

N	: 	Median	Min	Max	

Table 12.1.1.3 Dose intensity.

	N	Median	Min	Max
Cumulative dose (mg/m²)				
Dose intensity (mg/m² wk)				
Relative dose intensity (%)				

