12.7. Other tests and procedures

Table 12.7.1.1 Other tests and procedures.

Patient ID.	Cycle	Test Date	Test name	Result(Normal/Abnormal)	Findings

13. Appendix IV. Figures

NOTE: Figures here showed are examples and may vary in the format and will be showed for "all evaluable patients" and "all treated patients" when applicable.

Figure 13.1 Evolution of laboratory abnormalities (ANC, Platelets, AST, ALT,.....)

[figure not shown]

Figure 13.2 Overall survival.

[figure not shown]

Figure 13.3 Progression-free survival.

[figure not shown]
[figure not shown]
[figure not shown]

Figure 13.4 Duration of response.

[figure not shown]
Kaplan-Meier curve of duration of response (if any response is observed).

Figure 13.5 Waterfall plots.

[figure not shown]
Maximum tumor shrinkage in measurable lesions by RECIST v1.1 will be displayed. Additional graphs by histology or RECIST response will also be provided when applicable.

Figure 13.6 Spider plot (SLD)

(*) Sum of longest diameters for all target lesions.

Figure 13.7 Boxplot of LVEF evolution from BL.

Boxplot showing the change in LVEF from baseline, to worst value by cycle.

14. Appendix V. DB listings.

- -Listing 14.1.1. Cover
- -Listing 14.1.2. Study registration
- -Listing 14.1.3. Demography
- -Listing 14.1.4. Pregnancy test
- -Listing 14.1.5. Prior history
- -Listing 14.1.6. Ewing sarcoma history
- -Listing 14.1.7. Prior anticancer therapy: surgery
- -Listing 14.1.8. Prior anticancer therapy: radiotherapy
- -Listing 14.1.9. Prior anticancer systemic therapy: chemotherapy/biological therapy
- -Listing 14.1.10. Drug administration
- -Listing 14.1.11. Hematology laboratory values
- -Listing 14.1.12. Biochemical laboratory values
- -Listing 14.1.13. Other metabolic laboratory values
- -Listing 14.1.14. Physical examination
- -Listing 14.1.15. Performance status
- -Listing 14.1.16. Vital signs
- -Listing 14.1.17. Electrocardiogram
- -Listing 14.1.18. LVEF
- -Listing 14.1.19. Troponin I
- -Listing 14.1.20. Other tests and procedures
- -Listing 14.1.21. Adverse events (including signs and symptoms)
- -Listing 14.1.22. Concomitant therapy/procedures
- -Listing 14.1.23. Antiemetic prophylactic medication
- -Listing 14.1.24. Tumor evaluation
- -Listing 14.1.25. Radiological evaluation response assessment by cycle
- -Listing 14.1.26. Clinical evaluation response assessment by cycle
- -Listing 14.1.27. Overall response assessment by cycle
- -Listing 14.1.28. Best overall response

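### SAP 5.3: the exposure formula counts a completed last cycle as 6 weeks, not the 4 weeks the SAP sets, so full on-schedule dosing over n cycles gives a relative dose intensity of 2n/(2n+1) instead of 100%

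*SAP*

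**What the plan says.** The relevant definitions are all in SAP 5.3, under treatment exposure.

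- The last cycle's duration ("for the purpose of exposure calculations) will be 4 weeks".
- As a stated consequence of that, the length of exposure "will be calculated as the time between the day of the first dose and the day of last dose + 4 weeks (28 days"), reported in weeks.
- The date of last dose is the "Date of last treatment administration in the last cycle".
- A cycle is a period ("planned as 4 weeks plus the potential administration delays) between two dose infusions".
- Absolute dose intensity is cumulative dose over weeks of exposure. Intended dose intensity is "The planned dose per cycle divided by the planned weeks by cycle". RDI is the first as a percentage of the second.

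Protocol 7.2.2 gives 2 mg/m² on Days 1, 8 and 15 of a four-week cycle. SAP 7.4.2 counts delay from cycle start to cycle start: "the date of start of the actual cycle minus the date of start of previous cycle minus 28 days". The results appear in "Table 12.1.1.3 Dose intensity", which gives no other rule.

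**The concern.** Adding 28 days to the last infusion produces a 4-week last cycle only if that infusion opened the cycle. This schedule has three infusions per cycle, and SAP 5.3 defines the last dose as the final one given. The formula therefore does not deliver the 4-week last cycle from which it is said to follow, and the actual and intended intensities are measured on different clocks.

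A fully dosed patient would be reported with an RDI well below 100%, which a reader would take as missed, delayed or reduced treatment. The shortfall is not a constant offset. It depends on which day the last infusion fell and is largest for patients with few cycles, so patients with the same number of cycles and the same cumulative dose can receive different RDIs.

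Readers may also set the result beside the phase I figure at the recommended dose (median RDI 77.9%, range 33.2–103.2%; Protocol 1.2.5.1). The protocol does not say how that figure was derived, so comparability cannot be judged.

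**Working it through.** **Inputs.** 2 mg/m² per infusion, three infusions per cycle on Days 1, 8 and 15, cycle length 28 days (Protocol 7.2.2). Exposure, absolute, intended and relative dose intensity as in SAP 5.3. Infusions are assumed to be on their nominal days, with no delay or dose reduction.

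**Intended dose intensity.** 3 × 2 / 4 = 1.5 mg/m²/wk.

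**Last cycle under the formula.** Day 15 is 14 days after Day 1, so a completed last cycle counts as 14 + 28 = 42 days = 6 weeks. A last infusion on Day 8 gives 7 + 28 = 35 days = 5 weeks. Only a last infusion on Day 1 gives the stated 4 weeks.

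**Full dosing over n cycles.** The last infusion is 28(n−1) + 14 days after the first. Exposure is 28(n−1) + 14 + 28 = 28n + 14 days = 4n + 2 weeks. The cumulative dose is 6n mg/m². So RDI = [6n/(4n+2)]/1.5 = 2n/(2n+1).

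| Cycles | Dose (mg/m²) | Weeks | Absolute (mg/m²/wk) | RDI as written | RDI, 4-week last cycle |
|---|---|---|---|---|---|
| 1 | 6 | 6 | 1.000 | 66.7% | 100% |
| 2 | 12 | 10 | 1.200 | 80.0% | 100% |
| 3 | 18 | 14 | 1.286 | 85.7% | 100% |
| 4 | 24 | 18 | 1.333 | 88.9% | 100% |
| 5 | 30 | 22 | 1.364 | 90.9% | 100% |
| 6 | 36 | 26 | 1.385 | 92.3% | 100% |

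Counting days inclusively (one extra day) lowers these slightly, to 65.1%, 78.9% and 91.8% for 1, 2 and 6 cycles. Reading the last dose as Day 1 of the last cycle gives 100% for every n.

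**General factor.** The RDI as written equals the RDI on the 4-week basis times 4n/(4n+k), with k = 0, 1 or 2 for a last infusion on Day 1, 8 or 15.

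| Cycles | Day 1 | Day 8 | Day 15 |
|---|---|---|---|
| 1 | 1.00 | 4/5 = 0.80 | 4/6 = 0.667 |
| 2 | 1.00 | 8/9 = 0.889 | 8/10 = 0.80 |
| 4 | 1.00 | 16/17 = 0.941 | 16/18 = 0.889 |
| 6 | 1.00 | 24/25 = 0.96 | 24/26 = 0.923 |

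**Equal dose, different RDI.** Take two patients with two cycles and 10 mg/m² each.

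- Only Cycle 2 Day 15 missed: (35 + 28)/7 = 9 weeks; 10/9 = 1.111; RDI 74.1%.
- Only Cycle 2 Day 8 missed: (42 + 28)/7 = 10 weeks; 10/10 = 1.000; RDI 66.7%.
- On the 4-week basis both are (28 + 28)/7 = 8 weeks; 10/8 = 1.25; RDI 83.3%.

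**The case against.** The best defence is that the last dose was meant to be the dose opening the last cycle. The exposure sentence is presented as following from the 4-week rule. The cycle definition in the same bullet makes sense only from Day 1 to Day 1, and SAP 7.4.2 defines delay by the Day 1 infusion alone. On that reading the last cycle is exactly 4 weeks and full dosing gives 100%. This is probably what was intended, but the defined term says otherwise and nothing else in the SAP overrides it. A programmer who follows the text and one who infers the intent would produce different tables.

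A second objection is that little depends on the result. No decision or threshold is attached to RDI. Cycles given, cumulative dose, delays, skipped doses and reductions are tabulated separately, and RDI can be recomputed from "Listing 14.1.10. Drug administration" (SAP Section 14, Appendix V). That stands and limits the importance of the point.

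Third, the tabulated patients are idealised. The bias is nil when the last infusion is a Day 1, and for full dosing it has fallen to 7.7 percentage points by six cycles. Tumour evaluation is every other cycle with a window of one week either way (Protocol 3), so a patient who stops at the first evaluation may already have had Cycle 3 Day 1, in which case the formula works. The 80.0% figure therefore applies to a patient whose last infusion is Cycle 2 Day 15, and not to everyone who stops at the first evaluation.

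**Conclusion.** The point holds. The exposure formula, read with the SAP's own definition of last dose, contradicts the SAP's own 4-week last cycle. It understates absolute and relative dose intensity for every patient whose last infusion is on Day 8 or Day 15. For full on-schedule dosing, the shortfall after 2, 4 and 6 cycles is 20.0, 11.1 and 7.7 percentage points; after one cycle it is 33.3. These figures assume nominal infusion days with no delays or reductions.

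The consequence is confined to two of the three measures in SAP Table 12.1.1.3. The response rate, the two-stage decision, cumulative dose and the tables of delays, omissions and reductions are unaffected. The documents do not say how many patients will end on each infusion day, so the effect on the median RDI is unknown. The text should be corrected, but this is not a threat to the trial's conclusions.

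**What to change.** In SAP 5.3, define exposure duration as (Day 1 date of the last cycle − date of first dose + 28 days)/7 weeks. This applies the 4-week last cycle that the SAP already sets, keeps actual delays between earlier cycles in the denominator, and matches the start-to-start counting in SAP 7.4.2. As an optional clarification, state that a cycle runs between two consecutive Day 1 infusions.

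Keeping the present formula and dropping the 4-week statement would remove the contradiction in the text, but RDI for full dosing would stay below 100% unless the planned denominator also changed.

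The cost is one line of SAP text and the matching derivation code. Cycle start dates are already used for the delay calculation, so no further data are needed.

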6.1. Sample size determination

In this phase II trial, an optimum two-stage design to test the null hypothesis that the ORR is \leq 3% versus the alternative that ORR \geq 20% was selected. After testing the drug on 12 patients in the first stage, the trial will be terminated if there is not any responder. If the trial goes on to the second stage, a total of 29 patients will be studied, 12 from the first stage and 17 from the second stage. If the total number responding is less than or equal to 2 (two patients), the drug will be considered not interesting in the setting of patients treated with this disease and with this schedule.

This design has an expected sample size of 17.20 and a probability of early termination of 0.69 under the null hypothesis. If the drug is actually not effective, there is a 0.05 probability of concluding that it is (type I error). If the drug is actually effective, there is a 0.1 probability of concluding that it is not (type II error).

7. Statistical analysis

7.1. Treatment discontinuation and protocol deviations management

The study populations will be summarized and listed in Section 10 (Appendix I), including the number of patients in the following populations:

- Eligible patients.
- Included patients.
- All treated patients (safety population).
- Patients evaluable for the main endpoint (efficacy population).

Reasons for not belonging to any population will be detailed.

The accrual and study discontinuation details will be presented descriptively. The reasons for treatment discontinuation will be described by counts and percentages, overall and by number of cycles received. Reasons of treatment discontinuation other than disease progression will be detailed.

Reason for patient's study withdrawal will be also detailed. These may include:

- Study termination
- Patient refusal
- Investigator decision
- Lost to follow up
- Death
- Never treated
- Other reasons

A protocol deviation is defined as any departure from what is described in the protocol of a clinical trial approved by an Independent Ethics Committee/Institutional Review Board (IEC/IRB) and Competent Authorities. Therefore, it applies to deviations related to patient inclusion and clinical procedures (e.g., assessments to be conducted or parameters to be determined), and also to other procedures described in the protocol that concern the Good Clinical Practice (GCP) guidelines or ethical issues (e.g., issues related to obtaining the patients' Informed Consent, data reporting, the responsibilities of the Investigator, etc.).

Protocol deviations will be summarized for all patients. A summary table with the number of patients with inclusion/exclusion deviations will be presented per criterion. These patients will be listed with the criteria that are not met. Deviations with no effects on the risk/benefit ratio of the clinical trial will be distinguished from those that might have an effect on this risk/benefit ratio.

A study of the protocol deviations deemed relevant according to the Data Management Plan and Oncology review will be made following the International Conference on Harmonisation (ICH) guidelines. The protocol deviations will be listed by type of deviation, including (but not restricted to) the following categories:

- Patients not satisfying inclusion / exclusion criteria.
- Patients developing withdrawal criteria but not withdrawn.
- Patients receiving incorrect dose or at an incorrect schedule.
- Patients receiving forbidden concomitant treatment.
- Patients receiving treatment at the same dose and schedule but not satisfying criteria for treatment continuation.

